#### **4.7.2 Sampling Method**

All patients admitted to the inpatient departments of SHW, SHM and SHT during the study period will be included.

#### **4.8. Materials and Methods**

After getting approval from medical superintendent, patients with HIV-associated cryptococcal meningitis admitted to inpatient departments of SHW, SHM and SHT will be studied. They will be given IV infusion of amphotericin B (1 mg/kg/day) and oral flucytosine (100 mg/kg) for one week followed by oral fluconazole (1200 mg/day) for one week according to the hospital standard treatment guideline chosen by the physician depends on patient's clinical condition. Before giving treatment, informed consent will be obtained.

All patients meeting the inclusion criteria will be studied under the supervision of experienced physicians. Baseline data for assessing clinical effectiveness such as fever, convulsion and abnormal mental status and for safety such as hematological and biochemical parameters (hemoglobin, neutrophil, platelet, ALT, AST, serum creatinine and serum potassium level) will be noted from medical charts. Hematological and biochemical parameters will be graded according to DAIDS grading. Assessment of headache and its severity will be done by numerical rating scale under the supervision of physician.

Seven days and fourteen days after treatment, clinical effectiveness parameters such as headache, fever, convulsion, abnormal mental status and death will be reassessed. Clinical safety concerning hematological and biochemical parameters like hemoglobin, neutrophil, platelet, ALT, AST, serum creatinine and serum potassium level will also be reassessed and graded according to DAIDS grading by reviewing from patient's medical charts at seven and fourteen days. With regard to severity of headache, it will be documented by using numerical rating scale at weekly intervals for two weeks. Clinical effectiveness parameters (headache, fever, convulsion, abnormal mental status and death) and hematological and biochemical parameters will be described. The results will be documented for data analysis.

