## **1.2. Justification**

Cryptococcal meningitis is an AIDS-defining illness mostly caused by the fungus, *Cryptococcus neoformans*. In high-income countries, the use of amphotericin B in combination with a more expensive drug, flucytosine, is most effective for the management of cryptococcal meningitis; but access to flucytosine is severely limited in middle and low-income countries. In Myanmar, currently recommended regimen for cryptococcal meningitis are combination of amphotericin B with fluconazole. Although amphotericin plus flucytosine followed by fluconazole therapy is the currently preferred regimen in WHO treatment guidelines, it is not still commonly used in Myanmar clinical practice because of its limited availability. Therefore, the data regarding tolerability and clinical effectiveness of flucytosine are unavailable for Myanmar patients.

Although trials were carried out for investigating the effectiveness of flucytosine in the HIV population of Africa, the variability in drug response can occur

in Myanmar patients due to the racial and genetic differences and whether it is effective and safe for Myanmar people is a great curiosity question for clinicians and healthcare workers. In Myanmar, amphotericin plus flucytosine followed by fluconazole regimen will be supplied by National AIDS Program (NAP) and indicated in 2020. Thus, the documents for effectiveness and safety profile need to be established. This is the reason that the effectiveness and safety of amphotericin B with flucytosine and fluconazole combination therapy should be studied. From this study, it can provide information to physicians regarding the effectiveness as well as safety of those drugs in the management of cryptococcal meningitis in HIV patients.

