## 2.1.8. Induction, consolidation and maintenance antifungal treatment regimens

Table 1. WHO 2018 Induction, consolidation and maintenance antifungal treatment regimens (WHO, 2018)

Induction (adults, adolescents and children)		
Preferred regimen	amphotericin B deoxycholate (1.0 mg/kg/day) and flucytosine (100 mg/kg/day, divided into four doses per day) (one week), followed by 1 week of fluconazole (1200 mg/day for adults, 12 mg/kg/day for children and adolescents, up to a maximum dose of 800mg daily)	Strong recommendation, moderate certainty evidence for adults, low-certainty evidence for children and adolescents
Alternative	Two weeks of fluconazole (1200 mg daily for adults, 12 mg/kg/day for children and adolescents) + flucytosine (100 mg/kg/day, divided into four doses per day)	strong recommendation, moderate-certainty evidence
Alternative	Two weeks of amphotericin B deoxycholate (1.0 mg/kg/day) + fluconazole (1200 mg daily for adults, 12 mg/kg/day for children and adolescents up to a maximum of 800 mg daily)	strong recommendation, moderate-certainty evidence
Consolidation		
Consolidation	Fluconazole (800 mg daily for adults, 6–12 mg/kg/day for children and adolescents up to a maximum of 800 mg daily) for eight weeks following the induction phase	strong recommendation, low-certainty evidence
Maintenance (or secondary prophylaxis)		
Maintenance (or secondary prophylaxis)	Fluconazole (200 mg daily for adults, 6 mg/kg/day for adolescents and children)	strong recommendation, high-certainty evidence

In March 2018, WHO published “Guidelines for the Diagnosis, Prevention and Management of Cryptococcal Disease in HIV-Infected Adults, Adolescents and Children”. This guideline recommends a short-course (one-week)

induction regimen with amphotericin B deoxycholate and flucytosine followed by 1 week of fluconazole is the preferred regimen. In low- and middle-income countries, due to limited availability of flucytosine, alternative options of two weeks amphotericin B deoxycholate plus fluconazole are used depending on drug availability (WHO, 2018). Although guidelines exist for the antifungal management of cryptococcal meningitis, recommendations are based on limited data from RCTs, and in clinical practice treatment is highly variable due to drug costs, availability, and ability to monitor and manage drug-related toxicities (Perfect, 2010).

Table 2. Myanmar Specialist hospital guidelines for clinical management of Cryptococcosis in patients with HIV (2019)

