Initiation	IV Amphotericin 1 mg/kg plus Fluconazole 1200 mg IV/oral/ day for at least 2 weeks
Consolidation	Fluconazole 800 mg po od for 8 weeks
Maintenance	Fluconazole 200 mg OD until CD4 count rises to 200/mm  with ART

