### **4.6. Selection Criteria**

#### **4.6.1. Inclusion criteria**

1. Patients with HIV-associated cryptococcal meningitis, admitted to inpatient department of SHW, SHM and SHT during the study period
2. Patients of both sexes
3. Age above 14 years
4. Patients or caregivers who will give informed consent to participate in this study

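### Section 4.8 and the pro forma state one flat fluconazole dose for all participants above 14 years, and the protocol does not explain why this differs from the adolescent dose in its own Table 1

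*Combined protocol and SAP*

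**What the plan says.** **Study regimen.** Section 4.8 describes one week of amphotericin B and flucytosine, "followed by oral fluconazole (1200 mg/day) for one week". The sentence ends by saying that this is "according to the hospital standard treatment guideline chosen by the physician depends on patient's clinical condition". Part V of the pro forma (Annex 1) pre-prints fluconazole 1200 mg/day for one week. Neither place has an age or weight band.

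**Who is eligible.** Section 4.6.1 lists "Age above 14 years" with no upper limit and no separate rule for adolescents. The only exclusion in section 4.6.2 is pregnancy.

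**Where the regimen comes from.** Section 1.2 says that "amphotericin plus flucytosine followed by fluconazole therapy is the currently preferred regimen in WHO treatment guidelines", and gives its coming supply through the national programme as a reason for the study. Table 1 in section 2.1.8 sets out that regimen with doses. Its second week reads "followed by 1 week of fluconazole (1200 mg/day for adults, 12 mg/kg/day for children and adolescents, up to a maximum dose of 800mg daily".

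**The hospital guideline shown.** Table 2, in the same section, gives "IV Amphotericin 1 mg/kg plus Fluconazole 1200 mg IV/oral/ day for at least 2 weeks" as initiation treatment. It contains no flucytosine.

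**Flucytosine.** Section 4.8 has "oral flucytosine (100 mg/kg) for one week", and Annex 1 likewise gives 100 mg/kg. Table 1 gives 100 mg/kg per day in four divided doses.

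**The concern.** The study describes the effectiveness and safety of a named regimen, so a reader should be able to tell from the document what that regimen is for every eligible patient. For adults, section 4.8 and Table 1 give the same fluconazole figure. For anyone classed as an adolescent they do not, and no passage mentions or explains the difference.

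Two things are at stake. The first is clarity for the youngest eligible patients: the protocol prints two different fluconazole figures for the same drug sequence. The second is the meaning of the safety tables. Dummy Tables 8 to 11 treat all participants as one regimen group. If an adolescent's dose did differ from the pre-printed figure, the pro forma would not show it, because it has no field for body weight or for the dose actually given.

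**Working it through.** The plan gives no figure on this point to reproduce. The planned sample size of 27 (section 4.7.1) does not depend on it. The check compares the texts and then measures the gap between them.

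**Inputs from the documents**
- Section 4.8 and Annex 1, part V: fluconazole 1200 mg/day, flat.
- Table 1, adults: 1200 mg/day.
- Table 1, children and adolescents: 12 mg/kg/day, maximum 800 mg daily.
- Section 4.6.1: eligible above 14 years.

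**Input that is assumed.** The documents give no body weights, so a range of 35 kg to 66.7 kg and above is shown.

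**Step 1: the smallest possible gap, with no weight assumption.** The Table 1 adolescent figure cannot exceed 800 mg, so the ratio of the flat figure to it is at least 1200/800 = 1.5. The weight-based term alone would reach 1200 mg only at 1200/12 = 100 kg, and the maximum already applies from 800/12 = 66.7 kg. There is therefore no weight at which the two agree.

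**Step 2: the gap at assumed weights.** Table 1 figure = min(12 × weight, 800); ratio = 1200 / Table 1 figure.

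| Assumed weight (kg) | Table 1 adolescent figure (mg/day) | Ratio of 1200 mg/day to it |
|---|---|---|
| 35 | 12 × 35 = 420 | 2.86 |
| 40 | 12 × 40 = 480 | 2.50 |
| 50 | 12 × 50 = 600 | 2.00 |
| 60 | 12 × 60 = 720 | 1.67 |
| 66.7 and above | 800 (maximum) | 1.50 |

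**Step 3: does another passage settle it?** Section 4.8 points to the hospital guideline. The only hospital guideline reproduced, Table 2, is amphotericin plus fluconazole for at least two weeks, which is a different regimen. It does print 1200 mg without an age band, but it cannot be the source of the three-drug sequence. Section 4.5 defines the study population by the drug combination and gives no doses. Apart from section 4.8 and Annex 1, Table 1 is the only place that sets out this sequence in detail, and the only one that does so by age group.

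**Step 4: where a difference in exposure could show.** Fluconazole begins after the first week, so the day-7 laboratory values would largely precede it. Section 1.1 names liver-enzyme abnormalities as its reported effect. Any effect would therefore fall mainly on ALT and AST at day 14. The safety sample size rests on grade III/IV anaemia, and the protocol lists anaemia as an amphotericin B toxicity (sections 1.1 and 2.1.11). With 27 patients, one patient moves a percentage by 1/27 = 3.7 points.

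**The case against.** The strongest reply is that Table 1 is not a study rule. It stands in the literature review, it summarises an outside guideline, and no passage adopts its age-specific doses. Section 4.8 ties treatment to the hospital guideline and the physician's choice. Section 4.1 calls the study descriptive, and section 4.11 says that data are collected under routine management with no treatment restricted for the thesis. On that reading section 4.8 describes expected care and does not prescribe it.

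Most of this stands, and it rules out three stronger readings that a reader might infer:

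- *That the plan contains two operative dosing rules which cannot both be followed.* The documents do not support this, because only section 4.8 and Annex 1 describe the study's treatment.
- *That adolescents are expected, because dummy Table 5 has a row for age 20 or below.* That row is an empty band which would also hold young adults. Eligibility above 14 years is certain, but enrolment of any adolescent is not.
- *That some adolescents will be treated by Table 1 and others by section 4.8, and then pooled.* No passage says that anyone is treated by Table 1.

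The flucytosine wording is likewise an omission. Annex 1 and Table 2 also write amphotericin as 1 mg/kg without a time unit, and no passage states a conflicting flucytosine dose.

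The reply does not remove the inconsistency itself. Section 1.2 presents the regimen as the WHO preferred one, Table 1 is the protocol's own account of it, and the hospital guideline shown is a different regimen. The departure from the adolescent line is left unexplained.

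**Conclusion.** The point holds as an unexplained inconsistency between the study regimen as written and the source that the protocol presents for it. For a participant classed as an adolescent, the fluconazole figure in section 4.8 and Annex 1 is at least 1.5 times the figure in Table 1. That minimum needs no assumption about weight. The larger ratios, up to 2.5 at 40 kg and 2.86 at 35 kg, rest on assumed weights.

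The number affected is unknown and may be zero: the documents do not define adolescent, do not say where the adult line begins, and do not predict the age mix. Any effect on the results would be confined mainly to day-14 liver enzymes in that possibly empty group. The point is worth correcting because it concerns the dose written for the youngest eligible patients and costs almost nothing to settle. Nothing here shows which figure is right.

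**What to change.** Reconcile section 4.8, part V of the pro forma (Annex 1) and Table 1 in section 2.1.8 for participants classed as adolescents, and state the age at which the adult line applies. The treating physicians and the ethics committee should decide what governs; this review proposes no dose. It would help to identify the hospital guideline meant in section 4.8, since Table 2 shows a different regimen.

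As a minor editorial change, make the flucytosine units in section 4.8 and Annex 1 consistent with Table 1.

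The cost is a few lines of wording, with no added visits, tests or patients. Optionally, two fields on the pro forma, for body weight and fluconazole dose actually given, would let the report state what each participant received.

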### **2.1.11. Preventing, monitoring and managing antifungal toxicity**

#### Preventing, monitoring and managing antifungal amphotericin B toxicity

Drug toxicity and side-effects from amphotericin B therapy, especially hypokalaemia, nephrotoxicity and anaemia, are barriers to optimal induction treatment, safe administration of amphotericin B should be given priority and may require referral to a centre with access to a minimum package of preventing, monitoring and managing toxicity (WHO, 2018).

Table 3. Minimum package for preventing, monitoring and managing amphotericin B toxicity (WHO, 2018).

Pre-emptive hydration and electrolyte supplementation	
Adults and adolescents	One litre of normal saline solution with 20 mEq of potassium chloride (KCl) over two hours before each controlled infusion of amphotericin B and one to two 8-mEq KCl tablets orally twice daily. An additional 8-mEq KCl tablet twice daily may

	be added during the second week. If available, magnesium supplementation should also be provided (two 250-mg tablets of magnesium trisilicate or glycerophosphate twice daily, or magnesium chloride 4 mEq twice daily).
Monitoring (adults, adolescents and children)	
Serum potassium	Baseline and 2–3 times weekly (especially in the second week of amphotericin B administration)
Serum creatinine	Baseline and 2–3 times weekly (especially in the second week of amphotericin B administration)
Haemoglobin	Baseline and weekly
Management (adults, adolescents and children)	
Hypokalaemia	If hypokalaemia is significant ( $K <3.3$ mol/l), increase potassium supplementation to 40 mEq KCl by intravenous infusion and/or one to two 8-mEq KCl tablets orally three times daily. Monitor potassium daily.
Elevated creatinine	If creatinine increases by $\geq 2$ fold from the baseline value, increase pre-hydration to 1 L every eight hours and consider temporarily omitting a dose of amphotericin B. Once creatinine improves, restart amphotericin B at 0.7 mg/ kg/day and consider alternate-day amphotericin B. If creatinine continues to rise, consider discontinuing amphotericin B and continuing with fluconazole at 1200 mg/ day, especially if seven doses of amphotericin have been received. Consider fluconazole dose adjustment if significant renal impairment. Monitor creatinine daily.

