Severe anaemia	Transfusion should be undertaken if possible for severe amphotericin B–related anaemia (anaemia may also be a reason to discontinue amphotericin B prematurely in the second week of a planned two-week induction course of amphotericin B with fluconazole)
Additional notes:	

- Potassium replacement should not be given to people with pre-existing renal impairment or hyperkalaemia.
- Careful attention should be given to monitoring of intake and output of fluid and daily weight, especially among children.
- Flucytosine – because of concerns about bone marrow suppression, regular monitoring of full blood counts should be considered.
- The incidence of renal dysfunction and electrolyte disturbance is much less with liposomal amphotericin preparations, but renal function and electrolytes still need to be monitored

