#### **3.2. Objectives**

1. To find out the back-ground characteristics of patients with HIV-associated cryptococcal meningitis
2. To describe the clinical effectiveness of amphotericin B with flucytosine-fluconazole combination therapy by assessing clinical parameters at day 1, day 7 and day 14
3. To determine the severity of headache before and after treatment by numerical rating scale
4. To describe the clinical safety of amphotericin B with flucytosine-fluconazole combination therapy by assessing hematological and biochemical parameters by DAIDS grading at baseline, day 7 and day 14

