###### **(ii) Fever**

It is defined as rise in body temperature above 37 °C (98.6 °F) in the morning.

(iii) Convulsion

It is defined as a medical condition where body muscles contract and relax rapidly and repeatedly, resulting in uncontrolled actions of the body.

(iv) Abnormal mental status

It is defined as patients is somnolent, lethargy, disoriented and disruptions in perception and behavior.

(4) Clinical safety

Clinical safety will be assessed by laboratory defined adverse events. Adverse event is defined as any untoward medical occurrence in a subject to whom a medicinal product has been administered including occurrences which are not necessarily caused by or related to that product (Division of AIDS, 2017). Laboratory parameters (hematological and biochemical parameters) such as HGB, NEUT, PLT, ALT, AST, serum creatinine, serum potassium level will be graded according to DAIDS grading in appendix 3. Bone marrow suppression is defined as Grade 3 and 4 adverse events in one or more of anaemia, neutropenia and thrombocytopenia.

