#### 4.12. Algorithm

## 5. DUMMY TABLES

Table 4. Number of Cryptococcal meningitis in patients with HIV infection enrolled from individual specialist hospital

Hospital	Number (N)	Percentage (%)
Specialist hospital Waibargi		
Specialist hospital Mingalardon		
Specialist hospital Thakeyta		
Total		

Table 5. Distribution of age among study group of Cryptococcal meningitis in patients with HIV infection

Age (completed years)	Amphotericin B, Flucytosine plus Fluconazole group	
	Number	Percentage
≤20		
21-40		
>40		
Total		

Table 6. Distribution of gender among study group of Cryptococcal meningitis in patients with HIV infection

Gender	Amphotericin B, Flucytosine plus Fluconazole group	
	Number	Percentage
Male		
Female		
Total		

Table 7. Frequency distribution of headache among study group by Numerical rating Scale at day-1, day-7 and day-14

Days	Headache	Amphotericin B, Flucytosine plus Fluconazole group	
		Number	Percentage
day-1	No pain		
	Mild		
	Moderate		
	Severe		
	Intolerable		
Day-7	No pain		
	Mild		
	Moderate		
	Severe		
	Intolerable		
Day-14	No pain		
	Mild		
	Moderate		
	Severe		
	Intolerable		

Table 8. Clinical effectiveness of study group by assessing presence of headache, fever, convulsion, abnormal mental status and death at day-1, day-7 and day-14

Clinical parameters	Amphotericin B, Flucytosine plus Fluconazole group					
	Day 1		Day 7		Day 14	
	N	%	N	%	N	%
Headache						
Fever						
Convulsion						
Abnormal mental status						
Death						

Table 9. Laboratory-defined adverse events of amphotericin B, flucytosine and fluconazole at baseline and day-7 and day-14 by DAIDS grading

Days	DAIDS Grading	Hematological parameters & Biochemical parameters								Total
		Anaemia N (%)	Neutropenia N (%)	Thrombocytopenia N (%)	Elevated ALT level N (%)	Elevated AST level N (%)	Hypokalemia N (%)	Hyper creatinemia N (%)		
Baseline	Grade 1									
	Grade 2									
	Grade 3									
	Grade 4									
Day-7	Grade 1									
	Grade 2									
	Grade 3									
	Grade 4									
Day-14	Grade 1									
	Grade 2									
	Grade 3									
	Grade 4									

Table 10. Proportion of patients with grade 3 and 4 adverse events of hematological parameters at baseline, day-7 and day-14

	Grade 3 and 4 adverse events	Baseline		Day -7		Day -14	

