## VIII. Assessment of Convulsion

Days	Convulsion	
	Present	Absent
Day 1		
Day 7		
Day 14		

IX. Assessment of Abnormal mental status

Days	Abnormal mental status	
	Present	Absent
Day 1		
Day 7		
Day 14		

X. Laboratory (hematological and biochemical) parameters

hematological and biochemical parameters	Baseline	Day-7	Day-14
HGB (g/dL)			
NEUT ( $10^3/\mu\text{L}$ )			
PLT ( $10^3/\mu\text{L}$ )			
ALT (U/L)			
AST (U/L)			
Serum creatinine ( $\mu\text{mol/L}$ )			
Potassium (mmol/L)			

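### Laboratory toxicity is recorded only at baseline, day 7 and day 14, so Tables 9-11 give fixed-day prevalence and can understate the worst grade each patient reached

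*Combined protocol and SAP*

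**What the plan says.** Four places agree on the timing of laboratory safety data:

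- Objective 4 (section 3.2) describes safety "by assessing hematological and biochemical parameters by DAIDS grading at baseline, day 7 and day 14".
- Section 4.8 has the follow-up values "graded according to DAIDS grading by reviewing from patient's medical charts at seven and fourteen days".
- The pro forma, under "X. Laboratory (hematological and biochemical) parameters", has one cell per parameter for each of the three times. It has no cell for an interim value, a worst value, a transfusion or potassium replacement. Its treatment section pre-prints the regimen and has no place for an omitted dose.
- Table 9 is titled "Laboratory-defined adverse events of amphotericin B, flucytosine and fluconazole at baseline and day-7 and day-14 by DAIDS grading". Tables 10 and 11 use the same three times.

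Section 4.9 names the pro forma as the data collection tool, so a result with no field on it is not collected. Section 4.11 has adverse reactions passed to the physician for treatment but does not say that they are recorded or counted.

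Section 4.10, under clinical safety, gives a wider definition: "Adverse event is defined as any untoward medical occurrence in a subject to whom a medicinal product has been administered". It sets no day limit.

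Table 3 in section 2.1.11 reproduces a WHO 2018 monitoring package. It tests potassium and creatinine at "Baseline and 2–3 times weekly (especially in the second week of amphotericin B administration" and haemoglobin at baseline and then weekly. Section 4 does not adopt this package. It refers to the hospital treatment guideline and to routine management.

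**The concern.** The tables are headed as adverse events, but they will show who was at each grade on two particular days after baseline. A grade 3 or 4 abnormality that arose on another day and had fallen below grade 3 by the reading leaves no trace. Nor does one in a patient who died first. Amphotericin B and flucytosine are given in week 1, so the interval that matters most is from first dose to day 7, which is covered by one reading.

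Two things are at stake. Objective 4 would be answered with a narrower quantity than the protocol's own definition of an adverse event. And the rates quoted from the African trial in section 2.1.12, the trial that also supplies the planning proportion in section 4.7.1, are of events that developed during treatment. Fixed-day prevalence set beside those rates would tend to look more favourable for a reason unrelated to the drugs.

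**Working it through.** **The plan's own figure.** Section 4.7.1 uses n = z²p(1−p)/d².

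- Safety: 1.96² × 0.83 × 0.17 / 0.14² = 27.7.
- Effectiveness: 1.96² × 0.80 × 0.20 / 0.15² = 27.3.

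Both round up to 28; the plan states 27, a difference of one patient. The point here does not depend on it, and 27 is used below.

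**Direction of the error.** The plan's post-baseline record for a patient is the grade on day 7 and on day 14. The worst grade is the maximum over all days tested from first dose to day 14. The higher of the two readings is a maximum over a subset of those days, so it can equal the worst grade or fall below it, never exceed it. This fixes the direction for each patient's worst grade and for the count of patients affected. Percentages also depend on who has a value at each day, which the dummy tables do not show.

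**Which parameters are exposed.** Setting Table 3 beside the DAIDS thresholds in Annex 3:

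- *Creatinine.* Table 3 calls for action at a rise of at least 2-fold from baseline. Annex 3 puts a rise of at least 2.0 times baseline at grade 4. An episode that meets the trigger is therefore already grade 4. It leaves the grade 3/4 count, on the baseline criterion, only by falling below 1.5 times baseline before the reading.
- *Potassium.* Table 3 acts below 3.3 mmol/L ("increase potassium supplementation to 40 mEq KCl by intravenous infusion"). Annex 3 puts 3.0-3.4 at grade 1 and 2.0-2.5 at grade 3, so many corrected episodes would never have reached grade 3.
- *Haemoglobin.* Weekly testing roughly coincides with days 7 and 14. Losses come mainly from deaths before the reading or from unscheduled tests. Table 3 does provide for correction ("Transfusion should be undertaken if possible for severe amphotericin B–related anaemia").
- *Other parameters.* Table 3 says only that regular blood counts should be considered with flucytosine. It gives no schedule for ALT or AST.

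**Deaths.** Section 2.1.13 cites 9 of 63 patients dead at 2 weeks. If that rate applied here (an assumption), 27 × 9/63 = 3.9 patients would have no day-14 value.

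**Illustration of size.** Inputs: rate p = 0.062 (grade 3 or 4 creatinine, 1-week amphotericin B groups, section 2.1.12), taken as the true worst-grade rate; n = 27; and f, the share of events missed, which is assumed because the documents do not give it. Expected events seen = 27 × p × (1−f). Chance that none is seen = (1 − p(1−f))^27.

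| f (assumed) | Rate seen | Expected events seen | Chance of none |
|---|---|---|---|
| 0 | 6.20% | 1.67 | 0.18 |
| 0.25 | 4.65% | 1.26 | 0.28 |
| 0.50 | 3.10% | 0.84 | 0.43 |
| 0.75 | 1.55% | 0.42 | 0.66 |

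**The case against.** The strongest reply is that the plan does what it says. Objective 4 is to describe grades at three named times, the tables are labelled with those times, and no safety threshold or formal comparison is set. That stands: the tables mislead only if read as cumulative incidence. But they are headed as adverse events, section 4.10 defines those without a day limit, and the literature rates are of events that developed, so that reading is likely.

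It can also be said that interim results may not exist. This stands in part. Interim testing at the three hospitals is plausible but not stated. If they test only weekly, the fix adds little beyond deaths and unscheduled tests.

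The loss is also small in absolute terms. With f = 0.50, the creatinine example loses 0.84 of a patient (1.67 × 0.50), or 3.1 percentage points, against a planned precision of ±14 points for the safety proportion. That is fair. It argues for a low-cost fix, not for leaving the tables unlabelled.

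Three stronger readings are tempting and are not supported:

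- A reader might infer that the protocol itself schedules interim tests and corrections, so that treated events are routinely erased. Table 3 is cited background, and a treated event still at grade 3 or 4 on the reading day is counted.
- A reader might infer that transfusion hides much severe anaemia. The cited package tests haemoglobin only weekly, so it would not routinely generate a mid-week low value.
- A reader might infer widespread hidden severe hypokalaemia. The cited action level lies in grade 1, and section 2.1.12 reports grade 4 hypokalaemia in only one patient, under pre-emptive replacement.

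**Conclusion.** The point holds in a limited form. As written, the plan measures fixed-day prevalence of laboratory abnormalities, and any error in worst toxicity runs towards understatement. The exposure is clearest for creatinine and potassium, and mainly in week 1. For haemoglobin it rests on deaths before a reading and on unscheduled tests.

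The size is unknown. It depends on how often the hospitals test, how long abnormalities last and how many patients die before a reading. A reader might try to size it by assuming episode durations. With onset equally likely on days 2-7 and only the day-7 reading, a 2-day episode is missed in 4 of 6 cases (67%) and a 5-day episode in 1 of 6 (17%). The documents support neither duration, so no missed share should be quoted as a finding. The creatinine figures above are likewise an illustration: they assume that 6.2% applies to these patients and that f takes the values shown.

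Nor do the documents claim that the regimen will be declared safe. The risk lies in how the tables will be read. This is an inexpensive improvement to data capture and labelling, not a flaw that invalidates the design.

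**What to change.** Change the pro forma and the dummy tables, not the care:

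1. In pro forma section X, add for each parameter the worst value, with its date, from first dose to day 7 and from day 8 to day 14. Take it from all results already in the chart, including those of patients who die before the reading.
2. Record the number of tests per patient and parameter in each interval.
3. Record, with dates, any transfusion and any potassium replacement beyond routine pre-infusion supplementation. A plain intravenous potassium tick box would not discriminate, because the package in Table 3 gives potassium chloride before every infusion.
4. In Tables 9-11, report the worst post-baseline DAIDS grade per patient beside the fixed-day grades. Show the number of patients with a value at each day, and label the fixed-day figures as point prevalence.

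The cost is a little more chart abstraction per patient, with no new tests or visits. Test frequency will vary between patients, and more tests give more chance of finding a high grade, which is why item 2 is needed. Reported toxicity rates may be less favourable.
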